### **2.1.3.1 Primary efficacy endpoint(s)**

The primary efficacy endpoint is change in HbA1c (%) from baseline to Week 26.

### **2.1.3.2 Secondary efficacy endpoint(s)**

#### **Continuous secondary efficacy endpoints**

The continuous secondary efficacy endpoints are:

- Change in body weight from baseline to Week 26,
- Change in FPG from baseline to Week 26,
- Change in 7-point SMPG profiles from baseline to Week 26 (each time point and average daily value),
- Change in PPG and in blood glucose excursion in response to a standardized meal test in up to 50% subset of all patients from baseline to Week 26 at time points premeal, 10 min, 20 min, 0.5 h, 1 h, 1.5 h, 2 h, 3 h, 4 h post meal,
- Change in fasting insulin, proinsulin, and C-peptide from baseline to Week 26,
- Change in insulin, proinsulin, and C-peptide and associated excursion values in response to a standardized meal test in up to 50% subset of all patients from baseline to Week 26 at time points premeal, 10 min, 20 min, 0.5 h, 1 h, 1.5 h, 2 h, 3 h, 4 h post meal,
- Change in HOMA- $\beta$  and HOMA-IR from baseline to Week 26,
- Change in lipid profile (total cholesterol, triglycerides, LDL-C, and HDL-C) and free fatty acids, and Ketone bodies from baseline to Week 26,

For 7-point SMPG profiles, the mean daily (ie, average on 7 points) change from baseline to Week 26 will be analyzed. In addition, the change from baseline to Week 26 for each of the 7 points will be evaluated, respectively.

For FPG, only values assessed in fasting condition will be analyzed.

#### **Categorical secondary efficacy endpoints**

The categorical secondary efficacy endpoints are:

- Percentage of patients reaching HbA1c <6.5% (49 mmol/mol) at Week 26,
- Percentage of patients reaching HbA1c <7% (53 mmol/mol) at Week 26,
- Percentage of patients achieving  $\geq 5\%$  body weight loss at Week 26,
- Percentage of patients achieving  $\geq 10\%$  body weight loss at Week 26,
- Percentage of patients requiring rescue therapy during the 26-week randomized treatment period.

An algorithm for defining patients requiring rescue therapy is provided in [Section 2.5.8](#).

For further details on missing data handling, see [Section 2.5.3](#).

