9.1.1.2 Assessment method

For the eligibility and efficacy assessments of the study, HbA1c is measured by a certified level I National Glycohemoglobin Standardization Program (NGSP) central laboratory at time points according to the flow chart in [Section 1.2](#).

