9.2 SECONDARY ENDPOINTS

9.2.1 Secondary efficacy endpoints

- Change in body weight from baseline to Week 26.
- Percentage of patients achieving predefined HbA1c targets of <7% and <6.5% at Week 26.
- Percentage of patients achieving $\geq 5\%$ and $\geq 10\%$ body weight loss at Week 26.
- Change in FPG from baseline to Week 26.
- Change in 7-point SMPG profile from baseline to Week 26 (each time point and mean daily value).
- Change in PPG in response to a standardized meal test in up to 50% subset of all patients from baseline to Week 26 at time points premeal, 10mn, 20mn, 0.5h, 1h, 1.5h, 2h, 3h, 4h post meal, and associated glucose excursion values at these time points.
- Percentage of patients requiring rescue therapy during 26-week treatment period.
- Change in fasting insulin, pro-insulin, and C-peptide from baseline to Week 26, change in postprandial insulin, proinsulin and C-peptide in response to a standardized meal test in up to 50% subset of all patients from baseline to Week 26 at time points premeal, 10mn, 20mn, 0.5h, 1h, 1.5h, 2h, 3h, 4h post meal, and associated excursion values for each of the above parameters at these time points

- Change in β -cell function assessed by HOMA- β from baseline to Week 26.
- Change in insulin resistance assessed by HOMA-IR from baseline to Week 26.
- Change in fasting lipid profile (total cholesterol, triglycerides, LDL-C, and HDL-C), free fatty acids, and ketone bodies from baseline to Week 26.
- Changes in PD biomarkers assessments from baseline to Week 26 will be performed on the following variables:
 - Waist circumference, hip circumference, waist to hip ratio,
 - VAS for appetite/satiety score,
 - Fasting levels of adiponectin.

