### **2.1.3 Efficacy endpoints**

All biological efficacy assessments will be performed by a central laboratory. All scheduled measurements collected during the study will be used in the analysis, including those obtained after IMP discontinuation or rescue medication use.

Efficacy variables will be summarized in both standard international units and conventional units when applicable.

The baseline value for efficacy endpoints is the last available value prior to the first injection of IMP or the last available value on or before the date of randomization if not treated with IMP.

HbA1c is assayed at screening (Visit 1); at Visit 4 (Day 1) before first IP injection; at Visit 6 (Week 2); at Visit 8 (Week 4); at Visit 9 (Week 8); at Visit 10 (Week 14); at Visit 11 (Week 20); and at final assessment (Visit 12 at Week 26, primary endpoint assessment visit).

Body weight is measured at screening (Visit 1); at Visit 4 (Day 1) before first IP injection; at Visit 6 (Week 2); at Visit 8 (Week 4); at Visit 9 (Week 8); at Visit 10 (Week 14); at Visit 11 (Week 20); and at final assessment (Visit 12 at Week 26, primary endpoint assessment visit).

FPG is measured at a central laboratory at screening (Visit 1); at Visit 4 (Day 1) before first IP injection; at Visit 6 (Week 2); at Visit 8 (Week 4); at Visit 9 (Week 8); at Visit 10 (Week 14); at Visit 11 (Week 20); and at final assessment (Visit 12 at Week 26, primary endpoint assessment visit).

The self-monitored plasma glucose (SMPG) is measured over a single 24-hr period in the week before Visit 4 (Day 1) before first IP injection, Visit 10 (Week 14), and Visit 12 (Week 26, primary endpoint assessment visit).

Fasting insulin are measured at Visit 4 (Day 1) before first IP injection; at Visit 10 (Week 14); and at final assessment (Visit 12 at Week 26, primary endpoint assessment visit).

Following list of standardized meal test related measurements at premeal, 10 min, 20 min, 0.5 h, 1 h, 1.5 h, 2 h, 3 h, 4 h post meal at Visit 3 (Week -1); and at final assessment (Visit 12 at Week 26, primary endpoint assessment visit) in up to 50% subset of all patients:

- post-prandial plasma glucose (PPG) and associated glucose excursion
- postprandial insulin, proinsulin and C-peptide and associated excursion values

Pre-meal measurements of pro-insulin and C-peptide from the meal test will be used as fasting pro-insulin, and C-peptide values.

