### 2.4.4.2 Analyses of secondary efficacy endpoints

Descriptive statistics (number, mean, standard deviation, median, minimum, and maximum) will be provided by treatment for all continuous secondary variables at the scheduled visits.

All continuous secondary efficacy endpoints at Week 26 defined in [Section 2.1.3.2](#) will be analyzed using the same ANCOVA model with missing post baseline values imputed by placebo control-based MI method as described in [Section 2.4.4.1](#) to compare each SAR425899 dose group with placebo. For missing value at baseline, missing data will be imputed using the same MI under the MAR assumption as described in [Section 2.4.4.1](#). The model will include fixed effect terms of treatment groups (SAR425899 0.12 mg, SAR425899 0.16 mg, SAR425899 0.20 mg, placebo and liraglutide), randomization strata of screening HbA1c value ( $<8$ ,  $\geq 8\%$ ), randomization strata of Visit 4 (Day 1) BMI ( $<35.0$  kg/m^2,  $\geq 35.0$  kg/m^2), and country, and the covariate of baseline value. The three trend tests described in [Section 2.4.4.1](#) are planned on body weight only. For all continuous secondary efficacy endpoints, means and adjusted means of each treatment group will be provided, as well as adjusted mean and associated two-sided 95% CI of the differences between each SAR425899 dose group and placebo. The analyses include values at baseline and Week 26 (observed or imputed) regardless of treatment discontinuation or initiation of rescue therapy.

All categorical secondary efficacy endpoints defined in [Section 2.1.3.2](#) will be analyzed using a Cochran-Mantel-Haenszel (CMH) method stratified on randomization strata of screening HbA1c value ( $<8$ ,  $\geq 8\%$ ) and randomization strata of Visit 4 (Day 1) BMI ( $<35.0$  kg/m^2,  $\geq 35.0$  kg/m^2). The proportion in each treatment group will be provided, as well as the difference of proportions between each SAR425899 dose group and placebo with associated 2-sided 95% CI. For HbA1c ( $<6.5\%$ ,  $<7\%$  respectively at Week 26) and body weight ( $\geq 5\%$ ,  $\geq 10\%$  body weight loss respectively from baseline at Week 26) responders, all values at Week 26 will be used to determine whether a patient is a responder or not, even if they are measured after IMP discontinuation or rescue medication use. Patients who have no measurement at Week 26 will be treated as non-responders.

[figure not shown]

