### 2.4.4.3 Multiplicity issues

To control the type I error, a hierarchical testing procedure will be applied. The testing procedure will be performed to test the primary and secondary efficacy variables (HbA1c and body weight) by the following prioritized order. The test stop as soon as an endpoint is found not statistically significant at  $\alpha=0.05$  (2-sided).

Figure 1 - The hierarchical testing procedure

No multiplicity adjustment will be made on other secondary efficacy variables other than body weight.

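### Does the wrong mmol/mol figure beside the HbA1c <6.5% target change who counts as a responder?

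*SAP*

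**What the plan says.** SAP 2.1.3.2 lists two HbA1c responder endpoints, each with an SI value in brackets: "Percentage of patients reaching HbA1c <6.5% (49 mmol/mol) at Week 26" and "Percentage of patients reaching HbA1c <7% (53 mmol/mol) at Week 26".

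The protocol uses % alone. Protocol 9.2.1 has "Percentage of patients achieving predefined HbA1c targets of <7% and <6.5% at Week 26", and the synopsis and the objectives do the same. The responder analyses in Protocol 11.4.2.2 and SAP 2.4.4.2 also name the two targets only in %. SAP 2.4.4.2 adds that "all values at Week 26 will be used to determine whether a patient is a responder or not", and it counts patients without a Week 26 measurement as non-responders.

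Three other statements bear on the unit:

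- Protocol 9.1.1.2: "HbA1c is measured by a certified level I National Glycohemoglobin Standardization Program (NGSP) central laboratory".
- SAP 2.1.3.1: "The primary efficacy endpoint is change in HbA1c (%) from baseline to Week 26".
- SAP 2.1.3: "Efficacy variables will be summarized in both standard international units and conventional units when applicable".

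On testing, SAP 2.4.4.3 says "No multiplicity adjustment will be made on other secondary efficacy variables other than body weight".

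**The concern.** A responder endpoint is a cut-off, so an error in the cut-off can move patients across it. SAP 2.1.3.2 is where the SAP formally defines the endpoint, and two thresholds that should be identical are printed side by side. If 49 mmol/mol is looser than 6.5%, a programmer who used the bracketed figure would count some patients just above the target as responders. Each dose is compared with placebo by a CMH analysis that reports a difference in proportions with a 95% CI. Such an error could therefore reach reported comparisons, and it need not affect all groups equally. The call in SAP 2.1.3 for both unit systems makes it easy to imagine the SI figure being put to use.

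**Working it through.** **Inputs.** From SAP 2.1.3.2: the pairs 6.5% with 49 mmol/mol and 7% with 53 mmol/mol. Assumed, because the documents print no formula: mmol/mol = 10.93 × % − 23.5.

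**Check on the pair that should agree.** 10.93 × 7.0 − 23.5 = 53.01, which rounds to 53. The SAP's figure is reproduced.

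**The pair in question.** 10.93 × 6.5 − 23.5 = 47.55 (47.545 before rounding), which as a whole number is 48, not 49.

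**Does the choice of constants matter?**

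| Form of the conversion | 6.5% | 7.0% |
|---|---|---|
| 10.929 × (% − 2.15) | 47.54 | 53.01 |
| 10.93 × % − 23.50 | 47.55 | 53.01 |
| (% − 2.152) / 0.09148 | 47.53 | 53.00 |
| (% − 2.15) / 0.0915 | 47.54 | 53.01 |

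No variant reaches 49.

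**Can rounding explain it?** If 6.5 stands for anything from 6.45 to 6.549, the SI value runs from 46.98 to 48.08 across the variants, still short of 49. The two printed pairs imply a slope of (53 − 49)/0.5 = 8 mmol/mol per 1% HbA1c. Whole-number rounding of both figures allows (52.5 − 49.5)/0.5 = 6 to (53.5 − 48.5)/0.5 = 10. The conversion slope is 10.93.

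**What 49 would mean as a cut-off.** (49 + 23.5)/10.93 = 6.63%. The extra band is 6.63 − 6.50 = 0.13 percentage points of HbA1c.

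**Would the right whole number be a safe programming rule?** 48 back-converts to (48 + 23.5)/10.93 = 6.54%. A patient at 6.5% has an unrounded value of 47.55, which is below 48, so even the correct figure would misclassify that patient unless mmol/mol were rounded first. A whole-number bracket works as a label and not as the rule for derivation.

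**Which rule is operative?** Every place that defines or analyses the endpoint gives the target in %, and the SAP line with the error leads with <6.5%. The assay is NGSP-certified and the primary endpoint is in %. No supplied passage directs that responder status be derived from mmol/mol. With the % rule, the reclassified count is zero.

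**The case for a change.** The case for amending the SAP is that the wrong figure stands in the formal definition of a named secondary endpoint, next to an instruction to report in both unit systems. In the supplied text it is the only SI value for this target. A cut-off of about 6.63% would add patients at 6.5%, and those at 6.6% (48.64 mmol/mol) if values were left unrounded. If active-arm values cluster nearer the target than placebo values, the active arms would gain more. Correcting it costs one digit.

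The slip itself stands. So does the possibility that 49 is copied into a table heading or footnote.

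The rest is weaker. The instruction on units applies only where it makes sense, and a percentage of responders has no second unit. Any reclassification percentage would need assumed Week 26 means and SDs. The only HbA1c SD in the documents, 1.1%, is the sample-size figure for the change from baseline. Such a calculation would also have to leave out patients with no Week 26 value, who are already non-responders and cannot be reclassified. It would put a size on a programming choice that the documents do not call for.

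Two limits apply on either side. Without the outside formula the documents do not contradict themselves: two pairs always fit some line, and a simple proportion gives 53 × 6.5/7 = 49.2. Also, SAP Appendices B and D (the summary of analyses and the sample code) are not in the supplied text, so how the endpoint is restated or coded there cannot be seen.

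**Conclusion.** The bracketed 49 mmol/mol is a clerical slip for 48 (47.5 before rounding), on the assumption that the standard NGSP-to-IFCC conversion applies. The SAP's own 7% and 53 pair fits that conversion.

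The size of the effect under the plan as written is zero: no responder count, difference in proportions or confidence interval changes, because classification is in %. The sample size rests on a 0.7% difference in mean HbA1c change with SD 1.1%, and the type I error control covers HbA1c change and body weight. Neither involves this endpoint.

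An analyst following the plan would classify from the laboratory's % value. Anyone adding an SI equivalent to a table label would convert 6.5% and print 48. A sentence saying that the % value governs would only repeat what the analysis sections already specify. This is a slip to note when tables are labelled, and it gives no reason to amend the plan.

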7.2.1 Exclusion criteria related to study methodology

- E 01. At screening, patient's age < legal age of adulthood or >80 years.
- E 02. Screening HbA_{1c} <7.0% or >10.0%.
- E 03. FPG >15 mmol/L (270 mg/dL) measured by the central laboratory at screening (Visit 1), and confirmed (>15 mmol/L [270 mg/dL]) by a repeat test before randomization.
- E 04. Type 1 diabetes mellitus.
- E 05. BMI <25 kg/m² or >45 kg/m².
- E 06. Treatment with glucose-lowering agent(s) other than metformin currently or within the 3 months prior to screening.
- E 07. Previous insulin use, except for episode(s) of short-term treatment (≤15 consecutive days) for intercurrent illness or pregnancy or use of insulin within the last 6 months.
- E 08. History of acute metabolic complication, such as metabolic acidosis, including diabetic ketoacidosis, or hyperosmolar hyperglycemic state within 3 months prior to screening Visit 1.
- E 09. Hypoglycemic unawareness as judged by the Investigator.
- E 10. Untreated or uncontrolled hypothyroidism/hyperthyroidism.
- E 11. Use of systemic glucocorticoids for one week or more within the last 3 months, or anticipated need for systemic glucocorticoids during the study.

- E 12. Current or history of treatment with medications within the 3 months prior to screening Visit 1, that may cause significant weight gain: including systemic glucocorticoids (except for <7 days), tricyclic antidepressants, atypical antipsychotic and mood stabilizers (eg, imipramine, amitriptyline, mirtazapine, paroxetine, phenelzine, chlorpromazine, thioridazine, clozapine, olanzapine, valproic acid and its derivatives, and lithium) and weight loss (including but not limited to: orlistat, lorcaserin, pramlintide, metreleptin, topiramate and phentermine either alone or in combination, zonisamide and burproprion, either alone or in combination).
- E 13. Current participation in an organized diet reduction program or clinical trial of weight control (within the last 3 months prior to screening).
- E 14. History of prior surgical treatment for obesity or intent to pursue surgical treatment for obesity during the study period.
- E 15. Weight loss attempt, plans for major changes in physical activities or significant change in body weight in the 3 months prior to screening (Significant change in body weight is defined as ≥ 5 kg self-reported change during the previous 3 months).

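### The HbA1c responder analysis uses HbA1c only as a two-level screening stratum; for the <7% target, continuous baseline would recover modest precision, and patients already at target should be counted

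*SAP*

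**What the plan says.** SAP 2.1.3.2 lists two HbA1c responder endpoints: "Percentage of patients reaching HbA1c <7% (53 mmol/mol) at Week 26" and "Percentage of patients reaching HbA1c <6.5% (49 mmol/mol) at Week 26". SAP 2.4.4.2 analyses them by a "Cochran-Mantel-Haenszel (CMH) method stratified on randomization strata of screening HbA1c value" (<8, ≥8%) and Visit 4 BMI (<35, ≥35 kg/m²), and reports each dose's difference in proportions from placebo with a 95% CI.

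Response rests on the Week 26 value alone: "all values at Week 26 will be used to determine whether a patient is a responder or not". Neither a minimum fall from baseline nor a confirmatory value is required. "Patients who have no measurement at Week 26 will be treated as non-responders", and a sensitivity analysis also counts rescued patients as non-responders.

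Protocol 7.2.1 (E 02) excludes patients with "Screening HbA_{1c} <7.0% or >10.0"%, so the <7% target is the lower entry bound. That bound applies at screening. For analysis, "The baseline value for efficacy endpoints is the last available value prior to the first injection of IMP", which is planned at Visit 4, where no HbA1c limit applies.

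For the primary endpoint, SAP 2.4.4.1 adjusts for the same strata and also for continuous baseline HbA1c. Protocol 9.5 gives 7% as a guideline treatment target. Under SAP 2.4.4.3 the responder endpoints lie outside the testing hierarchy.

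**The concern.** A patient's distance from 7.0% at baseline largely decides whether a given change takes that patient below 7.0% at Week 26. The CMH strata see only which side of 8% the screening value fell, so patients at 7.0% and 7.9% are treated alike. With 30 placebo patients, it is avoidable to set aside a prognostic value that has been collected and is already in the ANCOVA.

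Interpretation is also affected. A patient at 6.9% at Visit 4 and 6.9% at Week 26 counts as a responder, and the plan does not count patients who start at target. A reader of the arm percentages cannot tell how much of the attainment was there at the outset.

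**Working it through.** **1. The plan's own figure.** Protocol 11.1 and SAP 1.3 give 60 v 30 patients, a difference of 0.7, SD 1.1, two-sided 5% and 80% power for the change in HbA1c. SE = 1.1 × √(1/60 + 1/30) = 0.246; 0.7/0.246 = 2.846; Φ(2.846 − 1.960) = 81.2%. The noncentral t with 88 df gives 80.4%. The figure reproduces. The documents state no power or expected rate for the responder endpoints.

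**2. Assumptions for the responder checks.** Only the SD of 1.1, the entry range 7.0–10.0% and the group sizes come from the documents.

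- Set A: HbA1c before selection has mean 7.8–8.4 and SD 0.8; visit-to-visit SD 0.15–0.35; Week 26 = Visit 4 value − effect + noise, with SD of change 0.6–1.1.
- Set B: usual level 8.0, SD 0.8, within-patient SD 0.3 (0.2–0.4 for rates); Visit 4 and Week 26 values scatter about the usual level, with SD of change 0.66 or 1.1.

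**3. Does HbA1c still predict response within a stratum?** In Set A with no effect, 18–32% of the <8% stratum are below 7% at Week 26, against 1–12% of the ≥8% stratum, so the planned strata separate much of the risk. Within the <8% stratum (Set B), the no-effect rate for screening values of 7.0–7.3 against 7.7–7.9 is 28–34% against 8–10% at SD 0.66, and 36–40% against 21–22% at SD 1.1. CMH leaves that gradient unused.

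**4. Precision for <7%.** Set A, mean 8.1, visit SD 0.25, 4,000 trials of 60 v 30. The stratified Mantel-Haenszel risk difference is compared with a logistic model (treatment, strata, continuous baseline) standardised to a risk difference.

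| SD of change | True effect | SE stratified | SE adjusted | Variance ratio |
|---|---|---|---|---|
| 0.6 | 0 | 0.0608 | 0.0566 | 0.865 |
| 0.6 | 0.7 | 0.0745 | 0.0685 | 0.845 |
| 0.8 | 0 | 0.0699 | 0.0670 | 0.918 |
| 0.8 | 0.7 | 0.0771 | 0.0731 | 0.899 |
| 1.1 | 0 | 0.0800 | 0.0781 | 0.953 |
| 1.1 | 0.7 | 0.0866 | 0.0841 | 0.943 |

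The variance falls by 5–16% overall and by 5–6% at SD 1.1. A further run gave 7–8% at SD 1.1 and 14–18% at SD 0.66. Set B, where Visit 4 is a noisier guide to Week 26, gave 3–8% across both SDs. In patients, a ratio of 0.943 is worth 90 × (1/0.943 − 1) ≈ 5 more, and 0.845 about 16 more.

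**5. Validity of CMH.** With no effect, the mean risk difference is 0.00 and CMH rejects in 4.6–5.0% of trials. At effect 0.7 and SD 1.1, both estimators average 0.166, and CMH rejects in 41.5% of trials against 37.0% unstratified.

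**6. Already at target at baseline.** Under no-effect assumptions, about 1–7% (Set A) or 1.5–8% (concern-level range with within-patient SD 0.2–0.4) are below 7.0% at Visit 4. At 1–8% that is 0.6–4.8 patients in an arm of 60 and 0.3–2.4 of 30 placebo patients. In the second range, 33–47% of them are below 7.0% again at Week 26 without any effect: 0.015 × 0.33 = 0.5% to 0.08 × 0.47 = 3.8% of all patients.

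**7. The <6.5% target.** Here the adjusted estimate gained little or nothing: the variance ratio was 0.86–1.08, 4–32% of trials had no placebo responder, and the large-sample CI covered only 83–91% under no effect.

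**The case against.** The strongest defence is that the endpoint measures attainment of a guideline target, by design. Change is measured by the primary endpoint with baseline as a covariate, the placebo arm shows the background rate, and a stricter <6.5% target is also planned. The strata already use HbA1c. The endpoint is an additional secondary outside the hierarchy, and the gain at the only SD in the documents is small. All of this stands, and it limits the point to a modest improvement.

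The defence also warns against the replacement model, rightly in part. A likelihood-ratio logistic test rejected in 6.3–8.3% of null trials. A score test held 4.9–5.4%, against 4.2–4.6% for CMH, with power of 48% against 45% at SD 1.1. Part of any raw power gain therefore reflects test size, and the variance ratios are the fairer measure. Empty placebo cells are a real risk: at a 6–11% response rate, the chance of no responder among 30 is 0.94^30 = 16% to 0.89^30 = 3%.

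A reader might infer that CMH ignores HbA1c; the <8/≥8% stratum shows otherwise. A reader might also infer that no-effect responders bias the comparison; they arise in every randomised arm, and step 5 shows neither bias nor inflated error. Nor do the documents support calling the threshold an error. An illustrative 0.5-point minimum fall would lower the no-effect rate only from 5.5–21% to 4.5–19%. At SD 1.1 the rate is 13–21%, but that SD may include real change over 26 weeks, so these patients cannot all be called chance responders.

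**Conclusion.** The point holds as a modest loss of precision and a gap in reporting. The planned CMH comparison is valid.

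For <7%, adjusting for continuous baseline HbA1c would remove about 5–18% of the variance of the risk difference, and about 5–8% at SD 1.1. Those figures rest on assumed baseline distributions and on Week 26 values that track the Visit 4 value; if both scatter about a usual level, the saving is 3–8%. For <6.5% no dependable gain was shown. About 1–8% of patients may start below 7.0%, again by assumption, so the arm percentages should be described as target attainment. The documents give no baseline HbA1c distribution, visit-to-visit SD or expected responder rate that would narrow these ranges.

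**What to change.** In SAP 2.4.4.2, keep both responder definitions, the ITT denominator, the non-responder rule and CMH, and add:

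- **For <7%:** a pre-specified analysis with treatment, the randomization strata and continuous baseline HbA1c, reporting the standardised risk difference of each dose versus placebo. Use a 95% CI suited to small samples, such as bootstrap or penalised likelihood.
- **Missing baseline:** use the imputation already set out in SAP 2.4.4.1. Few patients should need it, because eligibility requires a screening HbA1c and baseline is the last available pre-dose value.
- **Fallback:** rely on CMH if an arm has fewer responders than a number fixed before unblinding. State at the same time which <7% estimate leads.
- **For <6.5%:** CMH remains the lead.
- **A table by arm:** the number of patients already <7.0% and <6.5% at baseline.

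The cost is one extra model and one table, with no new data. Because CMH stays, the method in Protocol 11.4.2.2 is still carried out. The drawback is a second estimate to explain for a modest gain.
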